
Study Design and Methodology:
 
This is a phase 2b open-label study evaluating the efficacy and safety of aldoxorubicin administered at 230 mg/m² (170 mg/m² doxorubicin equivalent) intravenously on Day 1 every 21 days compared to topotecan administered either IV at doses of 1.5 mg/m²/day for 5 consecutive days starting on Day 1, and repeated every 21 days, or 4 mg/m² administered as a 30 min IV infusion on Days 1, 8 and 15 every 28 days. Subjects will be randomized 1:1 to receive either aldoxorubicin or topotecan. Treatment with granulocyte colony-stimulating factor (G-CSF) should be administered to all subjects as per investigator's clinical judgment or according to ASCO Guidelines (Appendix E).^[31] Note: aldoxorubicin, at higher doses, has been associated with >20% incidence of grade 3 or 4 neutropenia.
 
Subjects will visit the study site on Day 1 of each cycle. Safety monitoring, including AEs, a directed physical examination, laboratory evaluations (serum chemistry and complete blood count [CBC]), vital signs, weight measurements, Eastern Cooperative Group performance status (ECOG PS) and ECGs will be performed on Day 1 of each cycle (for all subjects). Subjects receiving aldoxorubicin will have blood drawn for serum electrolytes to evaluate the anion gap prior to each drug administration. They will have CBCs and serum chemistries on Day 15 (\pm 1 day) of each cycle as well. Cardiac function will also be followed periodically (per schedule of evaluations) with ECHO for subjects receiving aldoxorubicin. Treatment will continue until tumor progression is observed, subject asks to withdraw, or unacceptable toxicity occurs.
 
Tumor response will be monitored at baseline, every 6 weeks (\pm 5 days) from Cycle 1-Day 1 through week 36, and then every 12 weeks (\pm 5 days) until disease progression using the Response Evaluation Criteria in Solid Tumors (RECIST) 1.1 criteria.^[22] Overall survival, PFS, and PFS at 4 and 6 months will be evaluated. Objective response rate (ORR; complete response [CR] and partial response [PR]), disease control rate (ORR plus stable disease [SD] at 4 months) and quality of life (ECOG PS) will be assessed.
	

Name of Sponsor/Company: CytRx Corporation	
Protocol Number: ALDOXORUBICIN-P2-SCLC-01	Phase of Development: 2b
Study Population and Main Criteria for Inclusion/Exclusion:	
Inclusion Criteria:	
Subjects must meet the following criteria to be included in the study:	

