
 1. Age \geq18 years male or female. 2. Histological confirmation of SCLC. 3. Relapsed or refractory to no more than 1 course of a systemic therapy regimen and is incurable by either surgery or radiation. 4. Capable of providing informed consent and complying with trial procedures. 5. ECOG PS 0-2. 6. Life expectancy $>$8 weeks. 7. Measurable tumor lesions according to RECIST 1.1 criteria.^[22] 8. Women must not be able to become pregnant (e.g. post-menopausal for at least 1 year, surgically sterile, or practicing adequate birth control methods) for the duration of the study. (Adequate contraception includes: oral contraception, implanted contraception, intrauterine device implanted for at least 3 months, or barrier method in conjunction with spermicide.) 9. Males and their female partner(s) of child-bearing potential must use 2 forms of effective contraception (see Inclusion 8 plus condom or vasectomy for males) from the last menstrual period of the female partner during the study treatment and for 6 months after the final dose of study treatment. 10. Women of child bearing potential must have a negative serum or urine pregnancy test at the Screening Visit and be non-lactating. 11. Accessibility to the site that ensures the subject will be able to keep all study-related appointments. 	
Exclusion Criteria:	
Subjects meeting the following criteria will not be enrolled:	

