
Statistical Methods: In accordance with the intention-to-treat principle, all randomized subjects will be evaluated for efficacy. All subjects who receive at least 1 dose of study medication will be evaluated for safety.
 
Efficacy: The primary analysis of PFS will be carried out when 110 PFS events have occurred, approximately 6 months following the completion of enrollment of 132 subjects. Survival distributions will be estimated using the Kaplan-Meier method and the 2 groups will be compared using a two-sided, unstratified log rank test at the $\alpha=0.05$ level of significance.
 
Tumor response will be monitored at baseline, every 6 weeks (± 5 days) from Cycle 1-Day 1 through week 36, and then every 12 weeks (± 5 days) until disease progression. The percentage of subjects with CR or PR, or SD will be evaluated and the disease control rate (CR, PR and SD at 4 months) will be compared using Pearson's chi-square test, or if 20% or more of the expected cell frequencies are less than 5, Fisher's exact test. Investigator reported outcomes as assessed by the ECOG PS will be analyzed using analysis of covariance.
 
Subjects in each group will be stratified according to their initial PS (ECOG PS 0-1 vs 2) and whether they had progressed in less than or greater than 90 days after their initial chemotherapy.
 
Sample Size Justification: Power calculations and subject numbers were calculated based on the primary endpoint of PFS. Reviewing the literature for studies that have evaluated topotecan as treatment for patients that have relapsed or not responded to first line therapies, it is estimated that the median PFS for the topotecan group will be 3.5 months and that the median PFS for the aldorubicin group will be 6.5 months. Based on the use of a two-sided log rank test at the $\alpha=0.05$ level of significance, a total of 110 PFS events will be required for 90% power to detect this difference. Assuming an 18 month accrual period and a 6 month follow-up period after enrollment of the last subject, approximately 132 subjects will be needed to achieve the total of 110 PFS events.
 
Safety: The safety data will be summarized by treatment group. The treatment groups will be compared with respect to occurrence of each AE. Total number of AEs leading to withdrawal, and abnormal laboratory tests will be compared between groups using Fisher's exact test. Adverse events, ability to remain on assigned treatment (tolerability), and abnormal findings on physical examinations, vital signs, weight, ECG results, laboratory test results, and use of concomitant medications, will be assessed to characterize the safety profile of the treatment regimens. Descriptive statistics denoting the changes from baseline to the final assessment visit with respect to key laboratory parameters and vital signs will also be provided.
	

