
APPENDIX A: Schedule of Treatment and Evaluations

	Screening -28 Days	Cycle 1	Cycle 2	Cycle 3	Cycle 4	Cycle 5	Cycle 6	Cycle 7	Cycle 8 (repeat until off drug)	Day 15 (± 1 day) each Cycle	End of Treatment ¹⁴	Every 12 weeks ¹³	Follow Up ¹²
Signed ICF	X												
Review inclusion/exclusion	X	X											
Medical history ¹	X												
Physical examination	X	X	X	X	X	X	X	X	X		X	X	
Height (cm)	X	X ²											
Weight (kg)	X	X	X	X	X	X	X	X	X				
BSA calculation ²		X	X	X	X	X	X	X	X				
Vital signs ³	X	X	X	X	X	X	X	X	X		X	X	
ECOG PS	X	X	X	X	X	X	X	X	X		X		
CT/ MRI scan / tumor measurements ⁴	X ^{8a}			X ⁸		X ⁸		X ⁸			X ^{8, 10}	X ⁸	
ECG ¹⁸	X	X	X	X	X	X	X	X	X ¹⁸		X ¹¹	X ¹¹	
ECHO (with ejection fraction) ¹⁹	X		X		X		X		X ¹⁹		X ²²	X	
CBC w/differential & plts ^{5, 20}	X	X ¹⁶	X	X	X	X	X	X	X	X	X ¹¹	X ²¹	
Serum chemistries ^{6, 20}	X*	X ¹⁶	X	X	X	X	X	X	X	X	X ¹¹		
Urinalysis ⁷	X										X ¹¹		
Serum/urine pregnancy test	X												
Randomization		X ¹⁵											
Aldoxorubicin administration ¹⁷		X	X	X	X	X	X	X	X				
Topotecan		X	X	X	X	X	X	X	X				
Concomitant medications	X ⁹	X	X	X	X	X	X	X	X		X		
Adverse events		X	X	X	X	X	X	X	X		X		
Telephone follow-up													X

NOTE: All assessments must be performed within 72 hours of each specified time parameter, except Cycle 1 (see Section 6 for details).

*Arterial blood gas test, if needed, to confirm acid levels.

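### Inclusion criterion 8 guarantees female subjects no minimum contraception period after the final dose, while criterion 9 sets 6 months for males and their partners

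*Combined protocol and SAP*

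**What the plan says.** All references are to the Amendment 3 synopsis and its Appendix A grid.

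- **Inclusion Criterion 8 (women).** Eligible women are post-menopausal, surgically sterile "or practicing adequate birth control methods) for the duration of the study". No interval after the final dose is given.
- **Inclusion Criterion 9 (males and their female partners of child-bearing potential).** Two forms of contraception are required "during the study treatment and for 6 months after the final dose of study treatment".
- **Inclusion Criterion 10.** "Women of child bearing potential must have a negative serum or urine pregnancy test at the Screening Visit and be non-lactating". This is an entry condition only.
- **Study Design and Methodology.** "Subjects will be randomized 1:1 to receive either aldoxorubicin or topotecan", so both contraception criteria apply whichever drug is assigned. On stopping: "Treatment will continue until tumor progression is observed, subject asks to withdraw, or unacceptable toxicity occurs".
- **Statistical Methods.** The primary analysis takes place "when 110 PFS events have occurred, approximately 6 months following the completion of enrollment of 132 subjects". It is the only event-triggered analysis named there.
- **Appendix A.** The grid has columns for end of treatment, 12-weekly visits and follow-up, and a row for "Telephone follow-up". The pregnancy test is marked at screening only.

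Criteria 8 and 9 read the same way in the original protocol and in Amendments 1 and 2.

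**The concern.** The two criteria stand next to each other and concern exposure to the same two drugs, but they stop on different clocks. The one for males and their partners is counted from the last dose. The one for women, who receive the drug directly, is counted to the end of the study, and no supplied text says when that is for an individual subject.

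A woman could therefore comply fully with criterion 8 and still stop contraception sooner after a cytotoxic dose than the sponsor allows for males and their partners. What is at stake is a possible pregnancy soon after exposure. No treatment comparison is affected.

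**Working it through.** No planned figure bears on this point, so the check is a reading of the criteria with one line of algebra.

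**Step 1: define the cover.** For a given subject let D be the date of the final dose and E the date on which the study ends for her. Required cover after the final dose is:

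- criterion 8 (women): E − D
- criterion 9 (males and partners): 6 months, by construction

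**Step 2: look for a lower bound on E − D.**

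| Place | What it contributes |
|---|---|
| Criterion 8 | Names E as the end point but does not define it |
| Criterion 10 | Screening test and non-lactation; nothing after treatment |
| Study Design | D falls at progression, request to withdraw, or toxicity; no link between D and E |
| Statistical Methods | Times the PFS analysis; does not say the study closes or stays open |
| Appendix A grid | Shows follow-up after treatment, so E can fall well after D; sets no minimum |

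None of these gives a floor. E − D may be longer or shorter than 6 months.

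**Step 3: find circumstances in which E − D could be short.**

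- *Leaving the study on stopping treatment.* A request to withdraw is one of the three listed reasons for ending treatment. If the woman also leaves the study then, criterion 8 asks nothing further of her.
- *Closure soon after her last dose.* Treatment is open-ended. The sample-size section reads "Assuming an 18 month accrual period and a 6 month follow-up period after enrollment of the last subject". If the study closed about then, a woman enrolled last would have 6 months from enrolment to closure. Any final dose later than the day of enrolment would leave E − D below 6 months.

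Both are conditional. They show that the wording permits short cover, not that short cover is planned.

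**Step 4: check the remedy.** With a floor of 6 months, required cover becomes max(E − D, 6). This is never less than 6 months and never less than E − D, so no woman's period is shortened.

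**Step 5: check for statistical consequences.** The sample size uses median PFS of 3.5 and 6.5 months (hazard ratio 3.5/6.5 = 0.538), two-sided alpha 0.05 and 90% power. Schoenfeld's formula gives 110 events, as planned. No contraception period enters it.

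**The case against.** The strongest reply has four parts.

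**The record is incomplete.** For Amendment 3 only the synopsis and the Appendix A grid are available. The protocol body, the schedule footnotes and the consent text are the natural places for a post-dose period or a definition of end of study. This stands. What is established is that the synopsis criterion gives women no floor, not that the whole plan lacks one.

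**The study is wider than study treatment.** The list uses both terms, overall survival is to be evaluated, and telephone follow-up is scheduled. For many women criterion 8 may demand as much as criterion 9, or more. This also stands, but long cover for many is not a guaranteed minimum for each.

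**The routes to short cover are assumptions.** A request to withdraw ends treatment, but the text does not say that the subject leaves the study. An analysis date is not a closure date. Two stronger readings therefore fail:

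- A reader might infer that women are in fact uncovered from the final dose. The documents do not support this, because it requires full exit from the study on that day.
- A reader might use the accrual, follow-up and median PFS assumptions to calculate the share of subjects left with less than 6 months. Such a share would assume closure at the PFS analysis, would count men and women who cannot conceive, and would ignore deaths after progression. It would not measure the group at issue.

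**Six months is borrowed.** Nothing supplied shows that the period for males and partners is right for women, and the exposure routes differ. The length is indeed a clinical decision. Nor can a woman who has left the study be monitored, so a floor gives her an instruction and a basis for counselling, not oversight. Neither point argues against stating a period.

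**Conclusion.** The point holds as a low-severity patient-safety improvement. In the supplied Amendment 3 synopsis the guaranteed interval after the final dose is 6 months for males and their partners and unstated for female subjects. The conclusion rests on the wording of criteria 8 and 9 alone and needs no assumption about when the study closes.

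The number of women affected cannot be given. The documents do not say how many of the approximately 132 subjects would be women of child-bearing potential, and the number is probably small. Alpha, power, sample size and analysis are unaffected. If the protocol body or consent text already states a post-dose period for women, what remains is to make the synopsis criterion agree with it.

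**What to change.** Keep the present end point in criterion 8 and add a floor: contraception is to continue until the end of the study or until at least 6 months after the woman's final dose of study treatment, whichever is longer. The clinical team may set a longer floor. If the protocol body or consent text already gives a post-dose period for women, carry that period into criterion 8. Otherwise make the matching change there where needed.

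The cost is the wording of one inclusion criterion, consent text where it needs to match, and a slightly longer contraception commitment for a small, unstated number of women.

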
APPENDIX A: Schedule of Treatment and Evaluations

	Screening -28 Days	Cycle 1	Cycle 2	Cycle 3	Cycle 4	Cycle 5	Cycle 6	Cycle 7	Cycle 8 (repeat until off drug)	Day 15 (± 1 day) each Cycle	End of Treatment ¹⁴	Every 12 weeks ¹³	Follow Up ¹²
Signed ICF	X												
Review inclusion/exclusion	X	X											
Medical history ¹	X												
Physical examination	X	X	X	X	X	X	X	X	X		X	X	
Height (cm)	X	X ²											
Weight (kg)	X	X	X	X	X	X	X	X	X				
BSA calculation ²		X	X	X	X	X	X	X	X				
Vital signs ³	X	X	X	X	X	X	X	X	X		X	X	
ECOG PS	X	X	X	X	X	X	X	X	X		X		
CT/ MRI scan / tumor measurements ⁴	X ^{8a}			X ⁸		X ⁸		X ⁸			X ^{8, 10}	X ⁸	
ECG ¹⁸	X	X	X	X	X	X	X	X	X ¹⁸		X ¹¹	X ¹¹	
ECHO (with ejection fraction) ¹⁹	X		X		X		X		X ¹⁹		X	X	
CBC w/differential & plts ^{5, 20}	X	X ¹⁶	X	X	X	X	X	X	X	X	X ¹¹	X ²¹	
Serum chemistries ^{6, 20}	X*	X ¹⁶	X	X	X	X	X	X	X	X	X ¹¹		
Urinalysis ⁷	X										X ¹¹		
Serum/urine pregnancy test	X												
Randomization		X ¹⁵											
Aldoxorubicin administration ¹⁷		X	X	X	X	X	X	X	X				
Topotecan		X	X	X	X	X	X	X	X				
Concomitant medications	X ⁹	X	X	X	X	X	X	X	X		X		
Adverse events		X	X	X	X	X	X	X	X		X		
Telephone follow-up													X

NOTE: All assessments must be performed within 72 hours of each specified time parameter, except Cycle 1 (see Section 6 for details).

*Arterial blood gas test, if needed, to confirm acid levels.

CLINICAL PROTOCOL

TITLE: A Multicenter, Randomized, Open-Label Phase 2b Study to Investigate the Efficacy and Safety of Aldoxorubicin Compared to Topotecan in Subjects with Metastatic Small Cell Lung Cancer Who Either Relapsed or Were Refractory to Prior Chemotherapy

PROTOCOL NUMBER: ALDOXORUBICIN-P2-SCLC-01

STUDY DRUG: Aldoxorubicin

IND NUMBER: 75,478

EUDRACT NUMBER: 2014-002189-64

SPONSOR: CytRx Corporation
[name]
[name]
[contact]
[contact]

SAFETY HOTLINE: United States: [name]
Europe: [contact] [name]
or
[contact]

SAFETY FAX: United States: [name]
Europe: [name]

SAFETY EMAIL: [contact]

DATE OF PROTOCOL: June 20, 2014

AMENDMENT 1: September 10, 2014

AMENDMENT 2: January 26, 2015

AMENDMENT 3: February 17, 2016

CONFIDENTIAL

The information contained in this document is confidential and the proprietary property of CytRx Corporation. Any unauthorized use or disclosure of such information without the prior written authorization of CytRx Corporation is prohibited.

Protocol Synopsis

Name of Sponsor/Company: CytRx Corporation	

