Protocol Number: ALDOXORUBICIN-P2-SCLC-01	Phase of Development: 2b
Title of the Protocol: A Multicenter, Randomized, Open-Label Phase 2b Study to Investigate the Efficacy and Safety of Aldoxorubicin Compared to Topotecan in Subjects with Metastatic Small Cell Lung Cancer Who Either Relapsed or Were Refractory to Prior Chemotherapy	
Primary Objective: The primary objective of this study is to determine the efficacy of administration of aldoxorubicin compared to topotecan in subjects with metastatic small cell lung cancer (SCLC) who have relapsed or were refractory to prior chemotherapy, as measured by progression-free survival (PFS).	
Secondary Objectives: The secondary objectives of this study are to evaluate the efficacy of aldoxorubicin as measured by overall survival (OS), safety of aldoxorubicin compared to topotecan in this population assessed by the frequency and severity of adverse events (AEs), abnormal findings on physical examination, laboratory tests, vital signs, echocardiogram (ECHO) evaluations, electrocardiogram (ECG) results, and weight, as well as disease control rate and tumor response.	
Study Rationale and Significance: Aldoxorubicin (INNO-206; DOXO-EMCH) is a novel prodrug that binds covalently to albumin in the circulation. The drug is accumulated in tumors and doxorubicin is released in the tumor by cleaving the acid labile linker (EMCH) in the low pH tumor environment. This carrier-linked prodrug has demonstrated enhanced antitumor activity with reduced toxicity in several murine models when compared with free doxorubicin. Patients with metastatic SCLC who have failed prior chemotherapies have a poor prognosis with response rates of <10-25%, PFS of around 2-4 months and median OS of approximately 6-10 months, depending on the initial duration of response to first line treatment. Several chemotherapy regimens have been explored as palliative therapy for subjects with these patients and include such agents as topotecan (only approved agent in the US), topotecan plus platinum, cyclophosphamide + doxorubicin + vincristine (CAV) and amirubicin (not approved in US). However, these regimens can be quite toxic and have not significantly impacted either PFS or OS in these individuals. Aldoxorubicin may improve upon the activity of these drugs without an increase in toxicity as has been demonstrated in animal studies.	

Name of Sponsor/Company: CytRx Corporation	
Protocol Number: ALDOXORUBICIN-P2-SCLC-01	Phase of Development: 2b

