
12. Baseline QTc >470 msec measured by Fridericia's formula (QTcF) and/or previous history of QT prolongation while taking other medications. Concomitant use of medications associated with a high incidence of QT prolongation is not allowed.
 
13. History or signs of active coronary artery disease with angina pectoris within the last 6 months.
 
14. Serious myocardial dysfunction defined by ECHO as absolute left ventricular ejection fraction (LVEF) below the institution's lower limit of predicted normal.
 
15. Known history of HIV infection.
 
16. Active, clinically significant serious infection requiring treatment with antibiotics, anti-virals or anti-fungals.
 
17. Treatment with p-glycoprotein inhibitors such as cyclosporine A, elacridar, ketoconazole, ritonavir, saquinavir.
 
18. Major surgery within 30 days prior to date of randomization.
 
19. Substance abuse or any condition that might interfere with the subject's participation in the study or in the evaluation of the study results.
 
20. Any condition that is unstable and could jeopardize the subject's participation in the study.
	

Number of Subjects: Approximately 132 subjects with metastatic SCLC who have either not responded to or have progressed after treatment with no more than 1 prior systemic regimens will be randomized 1:1 (aldoxorubicin:topotecan) at approximately 40 study centers in the US and Europe. The randomization will be stratified according to their initial PS (ECOG PS 0-1 vs 2), and whether they had relapsed < or > 90 days after completing their initial therapy.
	

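### Optional improvement, not an error: the primary PFS log-rank ignores the relapse-timing stratum used at randomisation; stratifying by it would change power by about -0.5 to +3 points, most plausibly about +1

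*Combined protocol and SAP*

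**What the plan says.** The current text is the Amendment 3 synopsis. Under Number of Subjects it states: "The randomization will be stratified according to their initial PS (ECOG PS 0-1 vs 2), and whether they had relapsed" before or after a 90-day cut from the end of initial therapy. That makes four strata.

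Under Statistical Methods, Efficacy, the primary PFS comparison is explicit: "the 2 groups will be compared using a two-sided, unstratified log rank test", at the two-sided 0.05 level, once 110 PFS events have been reached. A little further on, the same section says "Subjects in each group will be stratified according to their initial PS (ECOG PS 0-1 vs 2", and adds the 90-day factor. It does not say whether this describes randomisation or analysis.

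The sample size paragraph assumes median PFS of 3.5 months on topotecan and 6.5 months on aldoxorubicin, and concludes that "a total of 110 PFS events will be required for 90% power to detect this difference".

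The one statement about prognosis is in Study Rationale and Significance: "PFS of around 2-4 months and median OS of approximately 6-10 months, depending on the initial duration of response to first line treatment". The documents give no hazard ratio for either stratification factor and no expected share of subjects in each stratum.

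**The concern.** Stratified randomisation balances the arms on the chosen factors. If those factors predict PFS, the between-arm difference varies less than an unstratified log-rank assumes. The test then rejects less often than 5% under the null and loses some power under the alternative. An analysis stratified by the same factors uses the balance that the design has created.

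PFS is the only endpoint with a stated power, and the factors are already recorded at randomisation. The question is therefore whether a small, nearly free gain in the primary analysis is being left unused, and under what conditions the gain is real.

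**Working it through.** **1. The plan's own figures.** Hazard ratio = 3.5/6.5 = 0.538 under exponential PFS. Schoenfeld events for two-sided 0.05, 90% power and 1:1 allocation: 4 × (1.960 + 1.282)² / (ln 0.538)² = 109.7, so 110. At 110 events the power is 90.1%. With 18 months of uniform accrual and 6 months of further follow-up, the event probabilities are 0.917 (topotecan) and 0.766 (aldoxorubicin), mean 0.841. This gives 132 × 0.841 = 111.0 events, or about 131 subjects for 110 events. The stated 110 and 132 both reproduce.

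**2. What the documents imply about relapse timing.** Assume the two ends of the 2-4 month range are the medians of the early and late relapse groups. Under exponential PFS this gives a relapse hazard ratio of 4/2 = 2. For a mixture of the two to have the planned 3.5-month control median, the early-relapse share p must satisfy

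p × 2^(-3.5/2) + (1 - p) × 2^(-3.5/4) = 0.5

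0.297p + 0.545(1 - p) = 0.5, so p is about 18.3%.

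A 30% share would give a control median of about 3.2 months, and a 50% share about 2.8 months. On this reading only a share near 18% agrees with the sample size paragraph.

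**3. Simulation.** From the documents: 132 subjects, 18-month accrual, analysis at the 110th event, treatment hazard ratio 0.538 within strata, control mixture median 3.5 months. Assumed: PS 2 in 20% of subjects, early relapse in 50, 30 or 18%, permuted blocks of 4 within strata, exponential PFS. Dropout and ties from the scan schedule are not modelled. With 40,000 replicates per scenario, the Monte Carlo standard error is about 0.16 point for power.

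Change in power from stratifying, in percentage points (50 / 30 / 18% early relapse):

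| Assumed prognostic effect | Relapse group only | Both factors |
|---|---|---|
| None | -0.5 | -1.3 |
| HR 1.25 for each factor | -0.1 / -0.3 / -0.4 | -0.8 / -1.0 / -1.0 |
| Relapse HR 2 alone | +3.2 / +2.2 / +1.4 | +2.4 / +1.4 / +0.5 |

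Separately coded simulations put the relapse-only change at -0.5 to -0.7 with no effect, +1.0 to +1.4 at 18%, and +2.9 to +3.2 at 50%. For two factors at 18%, the gain was as low as +0.3.

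**4. Type I error.** Unstratified: 5.0-5.2% when the hazard ratios are 1.25 or less, and 3.5-4.8% with HR 1.5 for each factor or with a relapse hazard ratio of 2. Stratified by relapse group: 4.4-5.4% across all scenarios.

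**5. How much is recovered size.** Calibrate each test to exactly 5% and compare again. At 18% early relapse and relapse HR 2, the relapse-only gain falls to about +0.2 point, and two-factor stratification loses about 0.4. Across all scenarios the two-factor change is only -1.4 to +1.1 points.

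**6. Sparse cells.** With PS 2 in 20% and early relapse in 18%, the smallest of the four strata expects 132 × 0.20 × 0.18 = 4.8 subjects. A two-factor test would need a pooling rule; a relapse-only test would not.

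**The case against.** The strongest reply is that nothing here is wrong. The unstratified test holds its level, the event count was calculated for it, and the choice is deliberate: the June 2014 protocol and Amendments 1 and 2 name a two-sided log-rank without qualification, and Amendment 3 adds that it is unstratified. All of this stands, and it is why the point is an optional improvement.

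A reader might infer a larger loss. If both factors had hazard ratios of 2 and half the subjects relapsed early, two-factor stratification would raise power from 83.6% to 87.8%, a gain of about 4.1 points. The documents do not support that reading: they say nothing about how prognostic performance status is, and a 50% share with medians of 2 and 4 months does not give the 3.5-month control median.

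The strata are also loosely defined. Number of Subjects counts from relapse after completing initial therapy, while Statistical Methods counts from progression after initial chemotherapy. Exactly 90 days belongs to neither group, and neither text places refractory subjects who never responded. A stratified primary test would inherit this ambiguity, so it has to be settled first.

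Timing matters too. The trial is open-label, and the title page carries "AMENDMENT 3: February 17, 2016", 19.9 months after the protocol date of June 20, 2014. The sample size paragraph was written "Assuming an 18 month accrual period and a 6 month follow-up period after enrollment of the last subject". Actual accrual is not given. A further change to the primary test could look data-driven unless its independence from results by arm is documented.

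**Conclusion.** The point holds as a low-priority improvement. Stratifying the primary log-rank by relapse group is worth about +1 to +3 points of power if the relapse hazard ratio is 2, and costs about 0.5 point if nothing is prognostic. The most document-consistent figure is about +1.0 to +1.4 points, and nearly all of that is test size the unstratified analysis leaves unused. Adding performance status as a second stratum gains about 0.5 point or less in that case and is not worth its complications.

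These sizes rest on assumed hazard ratios and stratum shares, and on reading the 2-4 month range as the two relapse groups.

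Three stronger inferences are not supported:

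- **Inflated type I error.** With prognostic factors the unstratified test is conservative.
- **A contradiction in Statistical Methods.** The sentence on stratifying subjects can be read as describing randomisation, so it needs clarifying only.
- **No stratified analysis planned at all.** Only synopses and schedule tables are available, and the full statistical section may name one.

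**What to change.** If it can be documented that nobody making the decision has seen PFS results by arm, amend the primary test to a two-sided log-rank stratified by relapse group as recorded at randomisation. Report the hazard ratio from a Cox model with the same stratification, and keep the unstratified log-rank as a sensitivity analysis.

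If that cannot be documented, leave the primary test unchanged and name the stratified log-rank as a prespecified sensitivity analysis, unless the full statistical section already does.

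In both cases, use one definition of the relapse stratum in Number of Subjects and Statistical Methods, describing how it was applied at randomisation. State how exactly 90 days and refractory non-responders are classed, and say that the stratification sentence in Statistical Methods refers to randomisation (or to analysis, if that is meant).

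No new data are needed. Changing the primary test costs a documented amendment in an open-label trial and about 0.5 point of power if relapse timing proves not to be prognostic. The sensitivity analysis alone costs one line.

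### Does the ECOG performance status ANCOVA need a fixed study week and a descriptive label written into the plan?

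*Combined protocol and SAP*

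**What the plan says.** In the Amendment 3 synopsis, Statistical Methods (Efficacy), the whole provision for ECOG PS is: "Investigator reported outcomes as assessed by the ECOG PS will be analyzed using analysis of covariance". Covariates, visit and the handling of absent scores are not given. The same section opens with: "In accordance with the intention-to-treat principle, all randomized subjects will be evaluated for efficacy".

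ECOG PS is among the efficacy variables under Criteria for Evaluation, and Study Design and Methodology mentions it as quality of life. It is in neither the primary nor the secondary objectives.

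On timing, Study Design and Methodology says: "Subjects will visit the study site on Day 1 of each cycle". Cycles last 21 days on aldoxorubicin. On topotecan they last 21 days, or 28 days for the regimen "administered as a 30 min IV infusion on Days 1, 8 and 15 every 28 days". On stopping it says: "Treatment will continue until tumor progression is observed, subject asks to withdraw, or unacceptable toxicity occurs". The ECOG PS row of Appendix A is marked at screening, at each cycle and at End of Treatment. It is blank in the Day 15, 12-weekly and follow-up columns.

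The only final-visit convention is under Safety. It is descriptive and covers "changes from baseline to the final assessment visit with respect to key laboratory parameters and vital signs".

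**The concern.** An ANCOVA needs one score per subject at a defined time. Here scoring stops soon after treatment stops, and the plan expects treatment to last longer on aldoxorubicin. If the final-visit convention were borrowed for ECOG PS, or the last available score used, aldoxorubicin subjects would be scored later in their disease. Two arms with the same PS course could then appear to differ, to aldoxorubicin's disadvantage. Cycle number does not align the arms either, because topotecan cycles may be longer.

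At stake is a misleading between-arm result on a listed efficacy variable, scored by unblinded investigators. It could be read as a quality-of-life comparison of everyone randomized when it describes only those still being scored.

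**Working it through.** **Inputs from the synopsis.** Median PFS 3.5 (topotecan) and 6.5 months (aldoxorubicin); two-sided alpha 0.05; 90% power; 110 events; 132 subjects at 1:1, so 66 per arm; accrual 18 months plus 6 months. The documents give no rate of PS change.

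**1. The plan's own figure.** HR = 3.5/6.5 = 0.538. Schoenfeld events = 4(1.960 + 1.282)²/(ln 0.538)² = 110, as stated. With exponential PFS and uniform accrual the event probabilities are 0.917 and 0.766, mean 0.841. Then 110/0.841 = 131 subjects, and 132 subjects give 111 events. The planning medians are therefore a sound basis for what follows.

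**2. Visit alignment.** Day 1 falls at multiples of 3 weeks or of 4 weeks, so the schedules coincide at weeks 12, 24 and 36. Cycle 7 Day 1 is week 6 × 3 = 18 or week 6 × 4 = 24. The 6-weekly scans, by contrast, are counted "from Cycle 1-Day 1 through week 36" in both arms.

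**3. Who can still be scored.** Progression-free out of 66 = 66 × 0.5^(t/median):

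| Week | t (months) | Topotecan | Aldoxorubicin |
|---|---|---|---|
| 12 | 2.76 | 38.2 | 49.2 |
| 18 | 4.14 | 29.1 | 42.4 |
| 24 | 5.52 | 22.1 | 36.6 |

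These are upper bounds, since toxicity and withdrawal also end treatment. An assumed extra 5-10% per month leaves about 29-33 and 37-43 at week 12.

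**4. Size of the timing effect, if End of Treatment were used.** Mean exponential times to progression are 3.5/ln 2 = 5.05 and 6.5/ln 2 = 9.38 months, 4.33 months apart. An equal drift of 0.05, 0.1 or 0.2 points per month (assumed) gives a false difference of 0.22, 0.43 or 0.87 points.

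A fuller null simulation used one-point steps with an assumed median of 4-12 months each, death as a competing stop, and the same PS course in both arms. Rejection at nominal 5%, and the mean difference against aldoxorubicin, were:
- End of Treatment score: 7.7-14.6%, 0.05-0.14 points.
- Last on-treatment score: 10.2-25.5%, 0.05-0.18 points.
- Observed score at week 12: 4.1-6.5%, 0.00-0.05 points.

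Separately coded runs with other settings gave 7.4-14.1% and 9-20% for End of Treatment under the same kind of drift.

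**5. A different mechanism.** Let PS worsen by one point at progression in 25-50% of subjects (assumed), with no drift. End of Treatment rejection is then 4.6-5.2%. Adding slow drift (median 24 or 12 months per step) to the 50% case gives 5.1% and 6.5%. A worsening at progression does not remove the timing shift: adding 0.5 points at treatment end to every subject left the false difference at 0.36 points under 0.1 points per month. It adds scatter, and the shift that remains is set by the drift rate, which is unknown.

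**6. What the obvious repair costs.** Observed scores at week 12 lose at least 66 − 38 = 28 topotecan and 66 − 49 = 17 aldoxorubicin subjects, 45 of 132 (34%). With an assumed SD of 0.5-0.9, the difference detectable at 80% power rises from 0.24-0.44 (66 against 66) to 0.30-0.55 (38 against 49). If PS worsens only at progression, those still scored have not changed, so rejection is 0% by construction, even though aldoxorubicin delays the worsening. Carrying earlier scores, including End of Treatment scores, to week 12 gave 11-22% there. Under the drift null the carried analysis rejected in 4.2-7.4% of trials, against 4.1-5.8% for observed scores in the same runs, and it keeps all 132 subjects.

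**The case for a change.** The best argument for a change is that it would be cheap and preventive. In an open-label trial with an investigator-scored outcome, naming the time point beforehand removes a choice among analyses that can give different answers. Week 12 follows from the protocol's own cycle lengths, no visit is added, and the drug most exposed to the artefact is the sponsor's own. Against an End of Treatment analysis, week 12 also costs no power in the settings tried: 6-33% against 4-11% if aldoxorubicin slows worsening by the PFS ratio, and 27-63% against 9-37% if topotecan causes an early one-point worsening in 25%.

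Much of this stands. The text available names no time point, a common study week is better than a cycle number, and an uncapped last score would be a poor choice. Three things do not carry over into a required change:
- The inflated error rates belong to analyses the plan never states. The final-visit phrase concerns laboratory values and vital signs, and only descriptively.
- The file holds synopses and schedules. Appendix A points to a Section 6 and to numbered footnotes that are not reproduced, so a fuller rule may exist.
- The repair is disputable. Observed-only week 12 fits badly with evaluating all randomized subjects and misses worsening at progression, while carrying scores to week 12 performs about as well under drift and better under the other mechanism.

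**Conclusion.** No change to the plan is needed. The silence on timing is real in the text supplied, but it is the kind of detail a synopsis leaves to the protocol body or to the analyst. A competent analyst would count time from Cycle 1 Day 1, adjust for baseline PS and show how many subjects were scored in each arm.

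The possible harm is a false difference of 0.05-0.14 points and 7.7-14.6% rejection at nominal 5%. It arises only if the End of Treatment score is chosen and PS drifts with time at the assumed rates; the last on-treatment score would do somewhat worse. It shrinks towards 5% if PS worsens mainly at progression. Fixing observed week-12 scores would exchange that conditional bias for the loss of at least 45 of 132 subjects, unequally by arm, so statisticians could fairly disagree on the remedy. A descriptive label would alter no result, because the plan assigns this variable no alpha. The stated objectives, the sample size and the primary PFS test are unaffected.

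This rests on the planning medians, exponential PFS and assumed PS behaviour. The judgement would change only if a fuller document did specify an uncapped End of Treatment or last-score comparison.
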